## 6.12 Adverse Events Assessments

### 6.12.1 Adverse Events (AEs)

All AEs, whether observed by the Investigator, reported by the subject, determined from laboratory findings, or other means, will be recorded on the AE CRF.

- For subjects who participate in Part 1 only, all AEs occurring after assent has been given or the ICF has been signed until the last study visit (through the Study Follow-up Visit or Part 1 early termination) will be recorded.
- For subjects who continue directly into Part 2 from Part 1, all AEs occurring after assent has been given or the ICF has been signed until the last study visit (Part 2 Study Termination Visit/Part 2 Early Termination Visit) will be recorded.
- For subjects who complete Part 1 and re-enroll in Part 2, all AEs occurring after assent has been given or the ICF has been signed in Part 1 until the last Part 1 study visit (through the Safety Follow-up Visit) and all AEs occurring after assent has been given or the ICF has been signed in Part 2 until the last study visit (Part 2 Study Termination Visit/Part 2 Early Termination Visit) will be recorded.

Any new clinically significant condition with onset after the last Part 1 visit (Visit 16) until assent/consent is provided in Part 2 should be recorded as medical history.

An AE is any untoward medical occurrence associated with the use of a drug in humans, whether or not considered related to study drug or procedure. During the study, clinically significant adverse changes in clinical status, ECGs, routine laboratory tests, and physical examinations are considered AEs. Any subject complaint associated with such an abnormal finding will also be reported as an AE. Symptoms of narcolepsy are not considered as adverse events unless there is an exacerbation of the symptoms from baseline (Visit 1 for Part 1 and Visit 17 for subjects who re-enroll in Part 2).

Adverse events include, but are not limited to: (1) a worsening or change in nature, severity, or frequency of conditions present at baseline (Visit 1 for Part 1 and Visit 17 for subjects

Xyrem® (sodium oxybate) oral solution  
Clinical Study Protocol: 13-005 Amendment 5

Jazz Pharmaceuticals

who re-enroll in Part 2); (2) subject deterioration due to primary illness; (3) intercurrent illness; (4) drug interaction; and/or (5) abnormal clinically significant laboratory values.

Subjects should be questioned in a general way, without asking about the occurrence of any specific symptom. The Investigator should attempt to establish a diagnosis of the event based on signs, symptoms, and/or other clinical information. In such cases, the diagnosis should be documented as the AE and not the individual signs/symptoms.

Following questioning and evaluation, all AEs, whether believed by the Investigator to be related or unrelated to the study drug or procedure, must be documented in the subject's medical records, in accordance with the Investigator's normal clinical practice, and on the AE CRF. Each AE is to be evaluated for duration, intensity, seriousness, and causal relationship to the study drug or procedure. An AE is deemed to be a suspected adverse drug reaction if there is a reasonable possibility that the AE may have been caused by the drug (or medicinal product) or study procedure as defined in Code of Federal Regulations Title 21 CFR 312.32 [a] and ICH E2A II.A.2.

#### 6.12.1.1 Severity

Adverse events will be classified by the Investigator as mild, moderate, or severe as defined below. When the intensity of the AE changes over time, the change in intensity will be recorded on the AE CRF as a new AE.

Mild	Symptom(s) barely noticeable to subject or does not make subject uncomfortable; does not influence performance or functioning; prescription drug not ordinarily needed for relief of symptom(s) but may be given.
Moderate	Symptom(s) of a sufficient severity to make subject uncomfortable; performance of daily activities is influenced; treatment for symptom(s) may be needed.
Severe	Symptom(s) causes severe discomfort; symptom(s) incapacitate or significantly affect subject's daily life; treatment for symptom(s) may be given and/or subject hospitalized.

#### 6.12.1.2 Relationship to Study Drug or Procedure

The Investigator's assessment of an AE's relationship to study drug or procedure is part of the documentation process, but it is not a factor in determining what is or is not reported in the study. If there is any doubt as to whether a clinical observation is an AE, the event should be reported. The relationship or association of the study drug or procedure in causing or contributing to the AE will be characterized using the following classification and criteria:

Xyrem® (sodium oxybate) oral solution  
Clinical Study Protocol: 13-005 Amendment 5

Jazz Pharmaceuticals

Related or Suspected to be Related to Study Drug or Procedure
	
Some temporal relationship exists between the event and the administration of the study drug or procedure and the event is unlikely to be explained by the subject's medical condition, other therapies or accident.
 
The AE follows a reasonable temporal sequence from administration of the study drug or procedure and at least one of the following instances of clinical evidence:
 
 
• Follows a known or suspected response pattern to the study drug or procedure.
 
• Is confirmed by improvement upon stopping the study drug or procedure or decreasing the dose (dechallenge).
 
• Reappears upon repeated exposure (rechallenge) if medically appropriate.
 
 
There is a reasonable possibility that the study drug or procedure caused the event—i.e., there is evidence to suggest a causal relationship. In such case, the AE is considered an adverse reaction (AR). A suspected AR has a lesser degree of certainty about causality than an AR.

Not Related to Study Drug or Procedure
	
Event can be readily explained by other factors such as the subject's underlying medical conditions, concomitant therapy, or accident; or there is no temporal relationship between study drug or procedure and the event.
 
A reasonable possibility or clinical evidence that the study drug or procedure caused the event is lacking.

### 6.12.1.3 Immediately Reportable Experiences

The following events may occur during participation in this clinical study and must be reported immediately:

- Death or other serious AE (SAE)
- Pregnancy of a subject or subject's partner
- 3-fold or greater elevation above the upper limit of normal (ULN) of alanine aminotransferase (ALT) or aspartate aminotransferase (AST) accompanied by an elevation of serum total bilirubin greater than two times the ULN
- Liver enzyme (AST, ALT) value greater than or equal to 5 times the ULN

The events listed above must be reported within 24 hours of first knowledge of the event by study personnel to the appropriate Jazz Pharmaceuticals contact or designee. For immediately reportable experiences, the appropriate form (e.g., SAE Report Form, Pregnancy Form) should be completed as thoroughly as possible and signed by the Investigator or his/her designee before transmittal to Jazz Pharmaceuticals Drug Safety and Pharmacovigilance.

Xyrem® (sodium oxybate) oral solution  
Clinical Study Protocol: 13-005 Amendment 5

Jazz Pharmaceuticals

For SAEs, it is important that the Investigator provide his/her assessment of causality to study drug or procedure at the time of the initial report. If the Investigator's assessment of causality subsequently changes, then a follow-up SAE form must be submitted with a revised causality assessment.

Jazz Pharmaceuticals Drug Safety is required to expedite to global regulatory authorities reports of Serious Adverse Events, including Suspected Unexpected Serious Adverse Reactions (SUSARs), as per the US FDA Code of Federal Regulations, European Commission Clinical Trials Directive (2001/20/EC), and other country-specific regulations.

For the purposes of global expedited adverse event reporting for this clinical trial, the reference safety document for the determination of expectedness is the Investigator's Brochure for Xyrem (sodium oxybate) oral solution for Pediatric Narcolepsy.

#### **SERIOUS ADVERSE EVENTS**

An SAE is an AE that fulfills the following criteria, as per Title 21 CFR 312.32 and ICH E2A.II.B. SAEs must be reported to Jazz Pharmaceuticals or its designee using the SAE Form. The following are defined as SAEs and must be reported within 24 hours of being notified of the event:

- Is fatal (results in death)
- Is life-threatening (Note: the term "life-threatening" refers to an event in which the subject was at risk of death at the time of the event; it does not refer to an event that could hypothetically have caused death had it been more severe)
- Requires inpatient hospitalization or prolongation of existing hospitalization
- Results in persistent or significant disability/incapacity
- Is a congenital anomaly/birth defect
- Is medically significant or requires intervention to prevent one of the outcomes listed above
- Suspected transmission of an infectious agent via a medicinal product *[for EU sites only; EMA Guideline on Good Pharmacovigilance Practices (GVP) Module VI]*

Hospitalization is NOT considered an SAE if:

- It is planned prior to subject entering study
- It is for social reasons and respite care in the absence of any deterioration in the subject's general condition
- It is elective in nature and not related to worsening of an underlying condition
- The subject is treated in the emergency room only AND no 'other' criteria of seriousness apply

Xyrem® (sodium oxybate) oral solution  
Clinical Study Protocol: 13-005 Amendment 5

Jazz Pharmaceuticals

Important medical events that may not result in death, be life-threatening, or require hospitalization may be considered an SAE when, based on appropriate medical judgment, they may jeopardize the subject and may require medical or surgical intervention to prevent one of the outcomes listed above in the definition of an SAE. Examples of such medical events include allergic bronchospasm requiring intensive treatment in an emergency room or at home, blood dyscrasias or convulsions that do not result in inpatient hospitalization, the development of drug dependency or drug abuse, and the occurrence of suicidal ideation.

#### **PREGNANCY**

If a subject [or male subject's partner] becomes pregnant any time after the first dose of study drug until 30 days after the last dose of study drug, the Pregnancy Form should be used to report the pregnancy to Jazz Pharmaceuticals or its designee. Subject pregnancies must be followed until termination of pregnancy or for a minimum of 6 months following the birth of the child. If the pregnancy results in a child birth, the infant must be followed for a minimum of 6 months. The Infant Follow-Up Form should be used to report information regarding the status of the infant.

#### **6.12.1.4 Adverse Event Recording and Reporting**

Each individual AE is to be listed as a separate entry on the AE CRF. The Investigator will provide information about dates of onset and resolution, seriousness, severity, frequency, action(s) taken, outcome, and relationship to study medication.

Documentation of immediately reportable events will follow procedures described in [Section 6.12.1.3](#), Immediately Reportable Experiences.

The Investigator must report to Jazz Pharmaceuticals or its designee all AEs that occur during the study after the informed consent has been signed and assent has been given until the final study visit or early termination, regardless of their relationship to study drug.

If an Investigator becomes aware of an SAE within 30 days after the last dose of study medication, the event must be documented and reported as described in [Section 6.12.1.3](#).

#### **6.12.1.5 Follow-up of Adverse Events and Serious Adverse Events**

Adverse events assessed as not related to study drug or procedure, including clinically significant laboratory tests, ECGs, or physical examination findings, must be followed until the event resolves, the condition stabilizes, the event is otherwise explained, or the final study visit occurs, whichever comes first. AEs and SAEs assessed as related to study drug or procedure will be followed for as long as necessary to adequately evaluate the subject's safety, or until the event stabilizes, or the subject is lost to follow up. If resolved, a resolution date should be provided, and for SAEs, a follow-up SAE form must be submitted indicating the resolution date. The Investigator is responsible for ensuring that follow-up includes any supplemental investigations indicated to elucidate the nature and/or causality of the AE. This may include additional clinical laboratory testing or investigations, examinations, histopathological examinations, or consultation with other health care professionals as is practical.

## 6.13 Concomitant Medication Assessments

Subjects will be asked to refrain from taking the prohibited medications specified in [Section 5.7](#) from the time of Screening until completion of the study. If discontinuation of CNS depressants or any medication poses a safety risk to the subject, the subject should not be enrolled in the study.

All concomitant medications taken during the study will be recorded on the Concomitant Medications CRF with indication, total daily dose, and dates of drug administration.

## 6.14 Removal of Subjects from the Study or Study Drug

All subjects are free to withdraw from participation in this study at any time, for any reason, and without prejudice. The Investigator must withdraw any subject from the study if the subject or subject's parent(s)/guardian(s) requests to stop participating in the study.

The Investigator, Jazz Pharmaceuticals or its designee may remove a subject from the study at any time and for any reason.

If any of the criteria below are met during the study, study drug administration must be stopped and the subject discontinued from the study.

- Suicide risk reported or assessed by C-SSRS
- Clinically significant depression independent of narcolepsy symptoms
  - If the T-score is  $\geq 65$  on CDI 2SR[S], an evaluation of depression by the Investigator (if qualified as a mental health professional) or by the Investigator in consultation with a mental health professional must be performed to exclude clinically significant depression
- Any PSG parameters that indicate, in the judgment of the Investigator, a risk to the subject's safe continued participation
- Subject becomes pregnant
- A positive urine drug screen for benzodiazepines or drugs of abuse (if the subject takes prescribed amphetamines, a positive result for amphetamines will not exclude the subject) or any suspicion by the investigator of abuse or diversion of study drug
- A positive alcohol test
- 3-fold or greater elevation above the upper limit of normal (ULN) of alanine aminotransferase (ALT) or aspartate aminotransferase (AST) accompanied by an elevation of serum total bilirubin greater than two times the ULN
- Liver enzyme (AST, ALT) value greater than or equal to 5 times the ULN
- Experiences an intolerable AE that is related to the study drug and/or procedure
- Develops any clinically significant worsening in narcolepsy symptoms during the Stable-Dose Period
- Develops a clinically significant laboratory or ECG abnormality that is related to the study drug and/or procedure
- Requires a medication that is prohibited by the protocol, with the exception of short-term opioid or benzodiazepine use (see [Section 5.7](#))
- Does not follow guidelines or procedures specified in the protocol

Xyrem® (sodium oxybate) oral solution  
Clinical Study Protocol: 13-005 Amendment 5

Jazz Pharmaceuticals

- 
- Is lost to follow-up
  - Does not continue to meet certain entry criteria or meets certain exclusion criteria during the course of the study
  - Subject reaches his/her 18th birthday. Subjects who terminate from Part 2 of the study because they have reached 18 years of age will be considered to have completed the study.

All subjects who prematurely discontinue from the study should have all early termination assessments performed (see Section 6.14.1, Handling of Early Terminations).

The specific reason for the discontinuation should be carefully documented on the termination CRF. If assent or informed consent is withdrawn, the specific reason for withdrawing the assent or informed consent should be stated.

Adverse events resulting in termination will be followed to the satisfactory resolution and determination of outcome as ascertained by the Investigator (and/or Jazz Pharmaceuticals or its designee). The data will be recorded on the appropriate CRF.

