initiation dose defined in [Table 1](#), whichever is higher. Subjects will then be titrated up to their optimal dose as tolerated according to the Investigator's judgment (the maximum dose should not exceed the doses defined in [Table 1](#) or the stable dose prior to study entry, whichever is higher, and should not be greater than 9 g/night). Xyrem dose up-titration is allowed at no more than 1.5 g/night, and during dose up titration the Investigator must monitor tolerability, which includes AEs observed at night, such as confusion, respiratory depression, sleepwalking and other parasomnias; residual effect and AEs observed during daytime, such as confusion, somnolence, pronounced levels of depressed consciousness, depressed mood and suicidality, anxiety, abuse or misuse of Xyrem, and weight loss.

Subjects may take two equally divided doses or two unequally divided doses with the exception of PK nights (if applicable) when all subjects have to take two equally divided doses 4 hours apart. Xyrem dose adjustment due to tolerability and efficacy is permitted. Only doses that match the printed gradations (lines) on the dosing syringe are permitted.

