**Table 4 Estimated Blood Volumes for Assays in Part 1 – PK Subjects**

	Screening (Day -30 to -1) a	PK Night 1 b	PK Night 2 b	End of Stable- Dose (Visit 3)	End of Double- Blind (Visit 4)	Termination (Part 1 Early Termination or Visit 15)	Total
Clinical chemistry	7.5 mL	--	--	--	7.5 mL	7.5 mL	22.5 mL
TSH		--	--	--	--	--	
hCG		--	--	--	Included in Chemistry	--	
Girls <8 years old: LH, FSH, estradiol Boys <9 years old: LH, FSH, testosterone		--	--	--	--	Included in Chemistry	
Hematology	2 mL	--	--	--	2 mL	2 mL	6 mL
HLA DBQ1 602	3 mL	--	--	--	--	--	3 mL
GH, prolactin	--	--	--	3.5 mL	Included in Chemistry	Included in Chemistry	3.5 mL
IGF-1	--	--	--	3.5 mL	3.5 mL	3.5 mL	10.5 mL
Coagulation (Screening)	2.7 mL	--	--	--	--	--	2.7 mL
Pharmacokinetic samples	--	7 × 2 mL	7 × 2 mL	--	--	--	28 mL
Volume for flushing indwelling catheter	--	6 × 1 mL	6 × 1 mL	--	--	--	12 mL
Approximate total blood volume per subject	15.2 mL	20 mL	20 mL	7 mL	13 mL	13 mL	88.2 mL

a If needed, additional screening time may be granted with permission of the Medical Monitor.

b PK Night 1 and PK Night 2 will occur while subjects are on a stable dose of Xyrem during the study.

For subjects who continue directly into Part 2 from Part 1, no additional blood samples will be collected for clinical laboratory assays. Estimated blood volumes for subjects who re-enroll in Part 2 are listed in Table 5. The approximate total blood volume to be collected for study assessments in these subjects will be 9.5 mL.

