#### 7.5.4 Visits 24, 30, and 36 (Onsite)

- Record height and weight in ordinary indoor clothes (without shoes).
- Perform alcohol test and urine drug screens.
- Obtain urine sample for pregnancy test (only perform for female subjects who have reached menarche).
- Obtain vital signs (systolic and diastolic blood pressure, pulse/heart and respiratory rate, and body temperature) after the subject has been resting for at least 5 minutes.
- Record all AEs on the AE CRF.
- Record all concomitant medications on the concomitant medications CRF.
- Collect study drug dispensed at the previous visit and measure compliance.
- Dispense study drug. (Access IRT.) Provide instructions for dose administration and, if flavored diluent is requested and available, the preparation of study drug with flavored diluent to subjects/parent(s)/guardian(s). See [Section 6.10](#).
- Determine when the subject will be 18 years of age. Schedule the Part 2 Study Termination Visit to occur *prior to* the subject's 18th birthday.

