## 7.6.3 Part 2 Visits for Subjects Re-enrolling Who Require Titration

### 7.6.3.1 Visit 18 (Onsite) Subjects Re-enrolling Who Require Titration – Begin Titration (Week T1)

Titration is required for subjects who are re-enrolling after completing Part 1 of the study and have been off Xyrem for  $\geq 1$  month. For subjects who have been off Xyrem for less than 1 month, titration may also be required per the Investigator's judgment. Subjects will be titrated to Xyrem as described in [Section 3.1.2](#). The Part 2 Titration may last up to 10 weeks. Once it is determined that the subject has achieved clinical benefit in cataplexy and EDS while maintaining tolerability, the subject may remain on that stable dose through the remainder of the titration period. However, Xyrem dose adjustment due to tolerability and efficacy is permitted per the Investigator's judgment.

Follow the activities in [Section 7.6.2.1](#).

Xyrem® (sodium oxybate) oral solution  
Clinical Study Protocol: 13-005 Amendment 5

Jazz Pharmaceuticals.

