#### 7.6.3.2 Visits 18.1, 18.2, 19, 19.1, 20, 20.1 (Phone Calls) Subjects Re-enrolling Who Require Titration

Study activities for Titration Phone Visits 18.1 (Week T2 +3 days), 18.2 (Week T3 +3 days), 19 (Week T4 +3 days), 19.1 (Week T7 +3 days), 20 (Week T8 +3 days), 20.1 (Week T10 +3 days) are as follows:

- Record all AEs that occur after assent was given and the ICF was signed on the AE CRF.
- Record all concomitant medications that were taken after assent was given and the ICF was signed on the concomitant medications CRF.
- Determine if additional dose titration is necessary.
- Determine when the subject will be 18 years of age. Schedule the Part 2 Study Termination Visit to occur *prior to* the subject's 18th birthday.

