## 9.9 Safety Analysis

Safety will be assessed at time points specified in the schedules of events, as well as throughout the study. Safety assessments will include the following:

- Adverse event (AE) monitoring
- Vital signs
- Physical examinations (including weight and height)
- 12-lead ECG
- PSG parameters (including respiratory measures)
- Clinical laboratory tests (chemistry, hematology, and urinalysis)
- Assessments of growth and precocious puberty
- C-SSRS (Children's Since Last Visit version for subjects under 12 years of age and the Since Last Visit version for subjects 12 years of age and older) for emergent suicidality
- CDI 2:SR[S] for emergent or worsening depression
- MASC-10 for emergent or worsening anxiety
- Serum pregnancy tests (if applicable)

Xyrem® (sodium oxybate) oral solution  
Clinical Study Protocol: 13-005 Amendment 5

Jazz Pharmaceuticals.

Exploratory endpoint:

- CO2 monitoring (EtCO2 or TcCO2) in sites where monitoring is routinely performed and performance will not negatively impact study participation or PSG data integrity

A DSMB will review the safety data on a regular basis, including monitoring for the following AEs:

- Confusion
- Somnolence and more pronounced levels of depressed consciousness
- Respiratory depression
- Depressed mood and suicidality
- Anxiety
- Sleepwalking and other parasomnias
- Abuse and misuse of study drug
- Weight loss

Adverse events will be mapped to system organ classes and preferred terms using the Medical Dictionary for Regulatory Activities (MedDRA).

**To address Primary Objective 2 and Secondary Objective 3:** Safety will be summarized using descriptive statistics and reported separately for Part 1 and Part 2 as well as across the entire study (Part 1 and Part 2) for select analyses. Adverse events will be assessed for subpopulations including Xyrem naïve, subjects on Xyrem at study entry, Ages 7-11, and Ages 12-17, as applicable. When summarizing data across the entire study by subpopulations, subjects are analyzed according to their initial enrollment status. For Part 1, adverse events will also be summarized by treatment group and by dose. Safety analyses will also include an analysis of the nadir oxygen saturation level at each dose, and number and duration of any confirmed desaturations below 90%, 80%, 70%, 60% and 50% on PSG nights excluding the screening PSG. For Part 2, safety data will be summarized by Ages 7-11, Ages 12-17, and overall.

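### Part 2 schedules no C-SSRS after Visit 15, including during re-titration, although the Section 6.14 stopping rule runs throughout the study and names that scale

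*Protocol*

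**What the plan says.** Section 6.14 opens its list of removal criteria with "If any of the criteria below are met during the study, study drug administration must be stopped and the subject discontinued from the study". The first criterion is "Suicide risk reported or assessed by C-SSRS". The second is clinically significant depression, with an evaluation prompted by a CDI 2:SR[S] T-score of 65 or more. The list is not limited to Part 1: it includes a rule on subjects who leave Part 2 at age 18.

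For direct continuers, Section 7.5.1 and Appendix 22 place the C-SSRS at Visit 15 and nowhere later. Sections 7.5.2 to 7.5.5 (Visits 19 to 42) do not list it. For re-enrollers, Section 7.6 and Appendices 23 and 24 omit it at Visits 17 and 18, at the titration calls and at every later visit. On re-titration, Section 7.6.3.1 says "The Part 2 Titration may last up to 10 weeks". The six calls in Section 7.6.3.2 cover adverse events, concomitant medications, the date of the 18th birthday and one dosing item: "Determine if additional dose titration is necessary".

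Other Section 6.14 screens remain. Section 7.5.4 lists "Perform alcohol test and urine drug screens" and a urine pregnancy test at Visits 24, 30 and 36, and Section 7.5.5 repeats both at Visit 42. Section 9.9 lists the C-SSRS as the safety assessment for emergent suicidality and has the DSMB monitor "Depressed mood and suicidality".

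**The concern.** The stopping rule names a scale that subjects do not meet again for up to two years. In that time, Section 6.12.1 tells sites to ask about adverse events in general terms and not to probe for particular symptoms. A child who has suicidal thoughts but does not mention them meets no scheduled prompt, and the DSMB review receives only what was volunteered or noticed.

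Two features of Part 2 add to this. Re-titration follows Section 3.1.2, with the same Table 1 dose limits as Part 1, but mostly by telephone. Section 5.7 bars a class exemplified by SNRIs, SSRIs and TCAs in Part 1 and then says such therapies may be allowed in Part 2, so structured screening ends when these drugs may be introduced. Sections 3.1 and 3.2 give long-term safety monitoring as one of the two purposes of Part 2, the other being continued access.

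**Working it through.** **Scheduled contacts in Part 2.** The protocol states no total, so these are counted from Sections 7.5 and 7.6 and checked against Appendices 22 to 24.

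- Phone (Section 7.5.2): Visits 19, 20, 22, 23, 25, 26, 28, 29, 31, 32, 34, 35, 37, 38, 40, 41 = 16.
- Onsite (Sections 7.5.3 to 7.5.5): Visits 21, 27, 33, 39 = 4; Visits 24, 30, 36 = 3; Visit 42 = 1; together 8.

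| Group | Contacts after Visit 15 | C-SSRS scheduled |
|---|---|---|
| Direct continuers | 16 + 8 = 24 | 0 |
| Re-enrollers, no titration | 24 + 2 (Visits 17, 18) = 26 | 0 |
| Re-enrollers, titrated | 26 + 4 (Visits 18.1, 18.2, 19.1, 20.1) = 30 | 0 |

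These are maxima. They fall if Part 2 ends early (18th birthday or FDA decision), and by one if Visits 17 and 18 share a day.

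**Titration of 10 weeks.** In Part 1 (Sections 7.2.2 and 7.2.3) the C-SSRS is given at Visits 1.1 to 1.7 and Visit 2, which is 8 forms. Drug is first dispensed at Visit 1.1, so 8 − 1 = 7 follow the start of dosing. In Part 2, drug is dispensed at Visit 18 and six calls follow (18.1, 18.2, 19, 19.1, 20, 20.1), with 0 forms.

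**Longest nominal interval between forms.** In Part 1 it is Week 9 to Week 16 (Visits 5 to 6, Appendix 1.1), or 7 weeks. In Part 2 it is up to 24 months for a direct continuer.

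**Expected events.** Section 1.1.2 reports ideation coded in 5 and attempts in 4 pediatric patients over about 1,150 patient-years.

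- Ideation: 5 / 1,150 = 0.43 per 100 patient-years.
- Attempts: 4 / 1,150 = 0.35 per 100 patient-years.

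The protocol gives no Part 2 enrollment, so exposure is assumed. At 200 patient-years (100 subjects for 2 years, an upper bound) the expected numbers are 0.87 and 0.70. At 50 patient-years they are 0.22 and 0.17. These are spontaneously reported rates.

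**Time for the proposed forms.** Assume 5 to 10 minutes per negative C-SSRS; the protocol gives no figure for this scale.

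| Group | Forms | Minutes over Part 2 |
|---|---|---|
| Direct continuers | 8 | 40 to 80 |
| Re-enrollers, no titration | 8 + 1 = 9 | 45 to 90 |
| Re-enrollers, titrated | 9 + 6 = 15 | 75 to 150 |

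**The case against.** The best defence is that nothing here is inconsistent. Section 6.14 can be met by reported risk without any scale, and its depression criterion is a clinical judgement. It is one pooled list for the whole study, and other triggers also go unscheduled in Part 2: PSG, ECG and, for direct continuers, liver tests, since "no additional blood samples will be collected for clinical laboratory assays". Section 9.9 ties safety assessments to the schedules of events. The omission also looks deliberate. Exclusions 14 and 15, which refer to the C-SSRS and the CDI 2:SR[S], are not carried into re-enrollment and are replaced by exclusion 37, which relies on the investigator's determination. Contact is roughly monthly, extra visits are allowed (Section 3.1.8), suicidal ideation is an example of a serious adverse event, a referral plan is expected (Section 6.6.12), and the DSMB reviews safety. Subjects being re-titrated have already completed a year under screening.

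Most of this stands, and it rules out calling the point a contradiction. It does not supply a prompt. PSG, ECG and liver tests need equipment, an overnight stay or blood; the C-SSRS needs none of these and was given by phone in Part 1 (Sections 7.2.2 and 7.4.2).

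A reader might also infer from Section 3.1.5 that Part 2 drops an explicit titration instruction, because that section tells the investigator to watch for "residual effect and AEs observed during daytime, such as confusion, somnolence, pronounced levels of depressed consciousness, depressed mood and suicidality, anxiety". The documents do not support this. The instruction sits in a paragraph on subjects who entered the Double-Blind Period before Amendment 4 and are restarting at a reduced dose. Section 3.1.2, the titration text shared by both parts, names neither depressed mood nor suicidality. The titration difference lies in the scheduled forms.

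**Conclusion.** The gap is real and limited. After Visit 15 the C-SSRS is scheduled at 0 of at most 24, 26 or 30 contacts, and a re-titration of up to 10 weeks has 0 forms after dosing starts, against 7 in a 10-week Part 1 titration. A reader might infer that Section 6.14 cannot operate in Part 2. That goes too far, because the reported limb, clinical judgement, serious adverse event reporting and DSMB review all remain.

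The case does not rest on a high event rate. Under the postmarketing rates and assumed exposures, fewer than one event of each kind is expected. Section 1.1.2 also notes no completed suicide and no signal of a greater psychiatric risk than in adults. The case rests on the seriousness of a missed event, general-only questioning, the possible introduction of antidepressant-type drugs, and the low cost of a form sites already use. No planned analysis is affected. This is a cheap improvement worth making.

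**What to change.** Add the age-appropriate C-SSRS at these existing contacts:

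- Visit 17 for re-enrollers, to inform exclusion 37. Use the Since Last Visit version, or the Baseline/Screening version if re-enrollment is long after Visit 16.
- The six Part 2 titration calls: 18.1, 18.2, 19, 19.1, 20 and 20.1.
- Onsite Visits 21, 24, 27, 30, 33, 36, 39 and 42. The longest nominal interval then falls from up to 24 months to about 3 months.

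Update Sections 7.5.3 to 7.5.5 and 7.6.1 to 7.6.3, and Appendices 22 to 24. Leave the CDI 2:SR[S] out of Part 2, since Section 6.6.4 says it is not validated in pediatric narcolepsy and overlaps with its symptoms. State in Section 6.14 that depression in Part 2 is judged clinically.

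The cost is the form time shown above, with no new visit and no blood, plus a protocol amendment with ethics approval and data capture for the added forms. There is one further downside: Section 6.14 makes C-SSRS-assessed suicide risk a mandatory discontinuation, so more screening may remove some subjects from continued access, possibly including some false positives.
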